$[\text{CaCO}_3]$) as prepared and labelled by the UNM Hospital research pharmacist, [name]. Subjects will start on doses of Metformin 500 mg po BID, and then the dose will be titrated up to 1000 mg po q AM and 500 mg po q PM over the course of 1 month, as tolerated. Subjects assigned to receive CaCO_3 will receive 648 mg po BID, and then the dose will be titrated up to 1296 mg po q AM and 648 mg po q PM over the course of 1 month, as tolerated.

Study investigators will be blinded to treatment assignment, and the study randomization list will be maintained by [name]. It should be noted that because Metformin has a distinctive odor, it is not possible to fully blind this study. For the purposes of this pilot study, however, we will take advantage of the fact that the dosages and appearance of CaCO_3 tablets and metformin tablets are very similar, and because study investigators and data collectors will be blinded to treatment, we believe that the study design is adequately robust.

FDA Regulatory Considerations: Metformin has an excellent long-term safety record and is already FDA approved for utilization in prediabetes. As such, attainment of an FDA IND is not necessary for this study. CaCO_3 is being administered in a manner consistent with current guidelines: 1000 mg of elemental calcium are recommended per day for adults, and our dosage delivers 780 mg of elemental calcium daily

(<https://medlineplus.gov/magazine/issues/winter11/articles/winter11pg12.html>).

Table 1: Study Visit Summary		
Visit Number	Data Obtained	Blood Volume
1 (Screening)	Blood: A1c, Lyses, BUN, Cr, Fasting Glucose, AST, ALT. Urine Pregnancy. Anthropometrics: Height, Weight Other: Health History, Physical Exam, AUDIT Questionnaire	22 ml
2 (Week 0, Baseline)	Blood: A1c, Fasting BMP, Insulin, LC3, TFEB, Galectin-3, DNA Methylation. Anthropometrics: Height, Weight, Body Composition by BIA. Other: Health History, Physical Exam, Distribute Step Diary.	60 ml
3 (Week 4)	Blood: A1c, Fasting BMP, Insulin, LC3, TFEB, Galectin-3, DNA Methylation. Anthropometrics: Height, Weight. Other: Health History, Physical Exam, Step Diary, Pill Counts.	60 ml
4 (Week 12)	Blood: A1c, Fasting BMP, Insulin, LC3, TFEB, Galectin-3, DNA Methylation. Anthropometrics: Height, Weight, Body Composition by BIA. Other: Health History, Physical Exam, Step Diary, Pill Counts.	60 ml

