Data Analysis: For continuous variables (i.e.- A1c, Body Mass Index, HOMA-IR index, Body Composition, LC3 Score, TFEB Score, Total DNA Methylation, and Galectin-3 concentrations), we will analyze the change from baseline (Week 0) at Week 12 using a two-tailed unpaired *t*-test. Repeated Measures Analysis of Variance will also be performed using the 0, 4, and 12 week data with study drug as the grouping factor and study variable as the repeated factor. We will assume a moderate correlation of 0.7 for laboratory values obtained within subjects over time, and we will again compare responses in the subjects who received metformin with those who received placebo. Descriptive statistics comparing baseline characteristics of the study participants will employ the two-tailed unpaired *t*-test for continuous variables, or the Chi-Square or Fisher Exact test for frequency data, as appropriate.

Table 2: Study Outcome Measures		
Study Variable	What It Measures	Metformin Effect
Aim 1: LC3	This test quantitates intracellular autophagosome formation; a marker of autophagy.	Increase
TFEB	This test quantitates via qRT-PCR, changes in gene expression levels of TFEB-regulated genes.	Increase
Aim 2: Total DNA Methylation	This test quantitates the amount of methylated DNA in a 60 ng sample of isolated DNA from PBMCs relative to a methylated control sample.	Increase
Galectin-3	A regulatory molecule acting at various stages along the continuum from acute to chronic inflammation and fibrogenesis.	Increase
Aim 3: A1c	Average glucose concentration over 90 days.	Decrease
BMI	Body mass normalized to height.	Decrease
HOMA-IR Index	Insulin sensitivity using fasting glucose & insulin.	Decrease

PROTOCOL TITLE: A Double-Blind, Placebo-Controlled Trial of Anti-Aging, Pro-Autophagy Effects of Metformin in Adults with Prediabetes

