Sample Size Determination and Power: Primary outcome variables for this study are “increase in LC3 Score from baseline” for Aim 1, “increase in total DNA methylation” for Aim 2, and “decrease in A1c” from baseline for Aim 3. Secondary outcome variables (not powered) are TFEB score for Aim 1, Galectin-3 concentrations for Aim 2, and BMI and HOMA-IR index (using fasting glucose and insulin) for Aim 3. These outcome variables are summarized in **Table 2**. We will enroll 30 subjects into this study and assume a dropout rate of 20%, leaving 12 subjects per group for data analysis. Sensitivity analysis will also be performed with an “intention to treat” analysis using the last value carried forward for subjects who dropped out.

For Aim 1, with 12 subjects per group, a difference in change in LC3 Score from baseline of 8 ± 4 Dots Per Cell (DPC) for Metformin vs. 3 ± 4 DPC for Placebo can be detected in PBMCs using a two-tailed, unpaired *t-test* with $\alpha = 0.05$ and $\beta = 0.83$. Baseline LC3 score is assumed to be 2 ± 2 DPC and not different between groups. This hypothesized difference is typical of those observed in [name] previous *in vitro* studies.

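### The only stated handling of dropouts is last value carried forward, which is biased for early leavers and for A1c and is an unreliable check on the Week 12 t-test

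*Combined protocol and SAP*

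**What the plan says.** Section 3.1 (Sample Size Determination and Power) enrols 30 and will "assume a dropout rate of 20%, leaving 12 subjects per group for data analysis". It then adds: "Sensitivity analysis will also be performed with an “intention to treat” analysis using the last value carried forward for subjects who dropped out".

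For the continuous outcomes, section 3.1 (Data Analysis) states that "we will analyze the change from baseline (Week 0) at Week 12 using a two-tailed unpaired" t-test. It adds that "Repeated Measures Analysis of Variance will also be performed using the 0, 4, and 12 week data" and that "We will assume a moderate correlation of 0.7 for laboratory values obtained within subjects over time". Neither analysis has a rule for subjects with missing visits. The conditional ANCOVA has none either, and section 13.1, where the analysis plan belongs, has no text of its own.

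Outcome bloods are scheduled at Weeks 0, 4 and 12 (Table 1). Study drug is raised to "500 mg po q PM over the course of 1 month, as tolerated". Table 2 describes A1c as "Average glucose concentration over 90 days". The LC3 power statement expects the outcome to move in both arms: a change of 8 ± 4 "Dots Per Cell (DPC) for Metformin vs. 3 ± 4 DPC for Placebo". Section 15.3 plans to attempt a close-out visit for withdrawn subjects but does not say whether blood is drawn or how any values enter the analysis.

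**The concern.** The wording about 12 per group, with LOCF listed separately, implies that the Week 12 t-test is run on subjects with Week 12 data. The reader then needs a check that shows whether losing a fifth of the sample has distorted the result. LOCF is the only one offered.

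On the scheduled bloods it can carry only a Week 0 or a Week 4 value. A carried Week 0 value means zero change, although the plan expects non-zero change in both arms for LC3 and A1c. A carried Week 4 A1c is taken at about the end of titration and, on Table 2's description, averages over a period that is mostly before treatment. So LOCF can differ from a sound completer result for reasons unrelated to informative dropout. The study is meant to supply preliminary data for a larger proposal, so a diluted estimate could also mislead later planning.

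**Working it through.** A1c differences are given as the extra reduction on metformin.

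**1. The plan's own figures.** 30 × 0.8 / 2 = 12 per group. With 12 per group and two-sided α = 0.05, LC3 (difference 5, SD 4) has standard error 4 × √(2/12) = 1.633. The noncentral t on 22 df gives power 0.833. A1c (difference 0.5, SD 0.4) has standard error 0.163 and the same power. Both match the stated 0.83, so that figure rests on 12 completers per group.

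**2. Expected LOCF estimate.** Let d be the share lost in an arm, m that arm's planned Week 12 change, and f the share of m present in the carried value. The arm mean under LOCF is m × [(1 − d) + d × f]. This assumes that dropouts would have followed their arm's planned course. With equal d the difference D becomes D × [(1 − d) + d × f].

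- Loss before Week 4 (f = 0, d = 3/15): LC3 0.8 × 5 = 4.0 DPC; A1c 0.8 × 0.50 = 0.40. No time course is needed.
- Loss after Week 4, A1c: 0.40 + 0.2 × f × 0.50, which is 0.425, 0.45 and 0.475 for f = 0.25, 0.5 and 0.75. The documents do not give f; this range is assumed.
- Loss after Week 4, LC3: the same formula gives 4.25 to 4.75 DPC over that range, but nothing in the plan shows that f is below 1 for LC3.
- Unequal random loss, A1c, 4 metformin v 2 placebo, f = 0.5: 0.8667 × 0.7 − 0.9333 × 0.2 = 0.42.

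**3. Can LOCF show whether the completer result is sound?** Simulation for A1c: 15 per arm, correlation 0.7 between visits (the plan's value), visit SD 0.4 (the plan's baseline SD, giving change SD 0.4 × √0.6 = 0.31), f = 0.5, dropout after Week 4, true difference 0.50. Selection means that metformin subjects with a poor Week 4 response tend to leave; its strength is the correlation between response and the dropout score. Gap = completers minus LOCF.

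| Dropout (metformin v placebo) | Completers | LOCF | Gap |
|---|---|---|---|
| 3 v 3 random | 0.50 | 0.45 | 0.05 |
| 4 v 2 random | 0.50 | 0.42 | 0.08 |
| 4 v 2, weak selection (0.3) | 0.52 | 0.41 | 0.11 |
| 4 v 2, moderate selection (0.5) | 0.53 | 0.40 | 0.13 to 0.14 |
| 4 v 2, perfect selection | 0.56 | 0.37 | 0.19 |
| 2 v 4, perfect selection in both arms | 0.47 | 0.50 | −0.03 |

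Under 3 v 3 random dropout the gap has SD 0.057, so about 0.05 ± 1.96 × 0.057 = −0.06 to +0.16. The mean gaps under weak and moderate selection lie inside that range; only perfect metformin-only selection lies outside it.

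**4. Size against sampling error.** The t-test standard error here is 0.127. For balanced loss after Week 4 the LOCF shift at f = 0.5 is 0.05/0.127 = 0.39 SE. If all losses come before Week 4 it is 0.10/0.127 = 0.79 SE, or 0.10/0.163 = 0.61 SE on the plan's change SD of 0.4; for LC3 it is 1.0/1.633 = 0.61 SE. Completer bias under perfect selection is 0.065, about half an SE.

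**5. A likelihood-based estimate.** It gives 0.50 in every row of the table, because dropout there depends only on observed values. If 4 v 2 metformin dropout depends instead on the unseen Week 12 value (weak / moderate / perfect), the model gives 0.53 / 0.55 / 0.60, completers 0.54 / 0.57 / 0.63 and LOCF 0.44 / 0.45 / 0.47.

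**The case against.** LOCF is a sensitivity analysis, not the main test, in a self-described pilot. With balanced dropout it errs toward no effect: with 3 v 3 lost before Week 4 and both arms changing by 3 DPC, simulated type I error is 0.036. The likelihood model does not always win. When dropout depends on the unseen Week 12 value, LOCF ties with it under moderate selection (each 0.05 off) and is nearer under perfect selection (0.03 off against 0.10). At f = 0.75 LOCF is level or nearer in all three cases. All of this stands, although LOCF is nearer there only because two errors offset, which a reader could not know from the data.

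Three stronger readings are tempting and not supported:

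- That LOCF is biased at Week 4 for all three primary outcomes. The 90-day description applies to A1c alone. The expected placebo LC3 change could be complete by Week 4, and the methylation figures compare age groups rather than changes over time.
- That LOCF says nothing about the completer result. A gap of 0.19 under extreme selection does stand out, and the case where LOCF agrees with expectation while completers are off needs perfect selection in both arms, with a completer bias of only 0.03.
- That LOCF will create false positives. Type I error for LC3 reaches 0.079 or 0.137 only with 5 v 1 or 6 v 0 dropout and Week 0 carried. The documents give no dropout by arm, and section 18.1 lists gastrointestinal effects in both (about 20% on metformin, up to 30% on calcium carbonate).

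**Conclusion.** The concern holds, with limits. LOCF is the only stated handling of dropouts. For loss before Week 4 it is biased on the plan's own LC3 and A1c figures, by up to a fifth of the planned difference when 3 of 15 are lost per arm. For A1c it is also biased for loss after Week 4, by 0.025 to 0.075 points over the assumed time course. For LC3 and methylation carried from Week 4, the bias depends on a time course the documents do not give.

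As a check it is unreliable: the gap it produces under random dropout overlaps the gap under weak or moderate selection. The size is modest: with balanced dropout about half an SE or less over most of the assumed Week 4 range, and about 0.6 to 0.8 SE only if every loss comes before Week 4. These figures assume that dropouts follow their arm's planned course and that the t-test uses completers, which is an inference. The change is worth making because it is cheap, not because the trial's conclusion is likely to turn on it.

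**What to change.** 1. Keep the Week 12 change t-test, on which the stated power rests, and name its analysis set.
2. In place of the repeated measures ANOVA and LOCF, fit a mixed model for repeated measures to Weeks 4 and 12 in all randomised participants as randomised. Include baseline value, arm, visit and arm by visit, with unstructured covariance and small-sample degrees of freedom. Report the Week 12 arm difference and state the missing-at-random assumption. Subjects lost before Week 4 add nothing to this model and enter only through step 3.
3. Add a delta-adjusted analysis: impute missing Week 12 values, then shift them separately in each arm and in both directions, for example by 0 to 0.5 A1c points and 0 to 5 DPC. With 3 of 15 missing in an arm, the largest shift moves that arm's mean by 3/15 × 0.5 = 0.10 points or 3/15 × 5 = 1.0 DPC. With 4 of 15 it is 0.13 points, which covers the 0.10 model error found above. A methylation range (such as 21.9 − 18.2 = 3.7 points) would be illustrative only, since that is a cross-sectional age difference.
4. State that close-out blood values count as Week 12 only if drawn within the Week 12 window.

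Cost: protocol wording and slightly more analysis work; the Week 0, 4 and 12 bloods are already scheduled. The model relies on missing-at-random, which is why step 3 is needed. The precision gain is small (SE about 0.12 against 0.127) and comes mostly from baseline adjustment.

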Our long term goal is to develop a phase III study in response to a specific NIH FOA using high content screening of leucocyte LC3 puncta scores, qRT-PCR transcription factor EB (TFEB) scores, and assays of total DNA methylation and galectin-3, to gauge the magnitude of metformin's effects on autophagy and cell senescence as markers of aging in adults with prediabetes. This study will provide preliminary data for such a proposal and will also fill a knowledge gap regarding the use of validated biomarkers in this field. It will also contribute significantly to the overall anti-aging literature. The primary objective of this proposal is to validate the autophagy experimental design in humans by using leucocyte LC3, TFEB, Galectin-3, and total methylation of DNA scores as markers of autophagy activity and cell senescence.

1.2. State the hypotheses to be tested.

AIM 1: Demonstrate that metformin therapy will increase cellular autophagy as an inverse correlate of aging as measured by increases in LC3 and TFEB scores.

Hypothesis 1: In addition to beneficial effects on glycemia, body weight, and body composition, metformin therapy exerts beneficial effects on surrogate measures of autophagy and aging.

Primary outcome: Increased levels of LC3 in leukocytes.

AIM 2: Demonstrate that metformin therapy will mitigate evidence of aging as measured by increased DNA methylation and decreased serum galectin 3 among adults with prediabetes.

Hypothesis 2: Metformin therapy exerts beneficial effects on DNA methylation as measures of aging

Primary outcome: Increased DNA methylation in leukocytes.

AIM 3: Monitor the beneficial metabolic effects of metformin in adults with prediabetes. Hypothesis 3: Metformin therapy will elicit the expected beneficial effects on glycemia, body weight, insulin resistance, and body composition demonstrated in previous studies.

Primary outcome: Decreased A1c.

2. Background

2.1. Describe the relevant prior experience and gaps in current knowledge.

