LC3 is our primary outcome variable for Aim 1. During the process of autophagy, autophagosomes engulf cytoplasmic components and concomitantly, the cytosolic form of LC3 (LC3-I) is conjugated to phosphatidyl ethanolamine, resulting in the autophagosomal membrane-bound form (LC3-II). LC3-II is a widely used marker to monitor autophagosome formation by quantitation of the number of LC3-labeled puncta (autophagosomes, or “dots”) per cell detected by fluorescence microscopy. An increase in LC3 puncta formation denotes an increase in autophagic activity. The [name] Lab has employed this technique in many different cell types, including human monocyte-derived macrophage cells (MDMs). Here, MDMs from human subject donors will be cultured and adhered in full media in 96 well plates and then immunostained to detect endogenous LC3 using Anti-LC3 polyclonal antibody (MBL P036) and a secondary fluorescent antibody. Plates will then be imaged using a Cellomics HCS scanner. This device will automatically capture cell images while identifying and quantifying LC3 puncta according to pre-set parameters in the HCS Studio software. This approach eliminates the problems of user subjectivity inherent in conventional microscopy studies while generating sufficient data from many hundreds of cells for robust and reproducible studies.

For Aim 2, we will employ the Imprint Methylated DNA Quantification Kit (Sigma-Aldrich, St. Louis, MO). This kit quantitates the amount of methylated DNA in a 60 ng sample of isolated DNA from PBMCs relative to a methylated control sample. Gomes and colleagues described a study comparing the total DNA methylation of young (26.5 years) and older (70.8 years) healthy subjects. They found a pattern of relative DNA hypo-methylation among the older subjects: $18.2\pm1.6\%$ in the older subjects versus $21.9\pm3.0\%$ in the younger subjects [127]. With 12 subjects per group, we can detect a difference of this magnitude with $\alpha = 0.05$ and $\beta = 0.82$.

For Aim 3, with 12 subjects per group, a difference in change in A1c from baseline of $0.7\pm0.4\%$ for Metformin vs. $0.2\pm0.4\%$ for Placebo can be detected with using a two-tailed unpaired *t-test* with $\alpha = 0.05$ and $\beta = 0.83$. Baseline A1c is assumed to be $6.1\pm0.4\%$ and not different between groups.

Potential Challenges: If adherence to lifestyle modification is significantly different between groups, this could become an important confounder. If this occurs, we will perform a

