Primary outcome: Increased DNA methylation in leukocytes.

AIM 3: Monitor the beneficial metabolic effects of Metformin in adults with prediabetes. Hypothesis 3: Metformin therapy will elicit the expected beneficial effects on glycemia, body weight, insulin resistance, and body composition demonstrated in previous studies.

PROTOCOL TITLE: A Double-Blind, Placebo-Controlled Trial of Anti-Aging, Pro-Autophagy Effects of Metformin in Adults with Prediabetes

Primary outcome: Decreased A1c.

7.2. Describe any primary or secondary safety endpoints.

TFEB, scores, Galectin-3 levels, BMI, HOMA-IR, fasting glucose, step-counts, pill-counts, body composition, serum creatinine, history and physical exam.

7.3. Describe any exploratory endpoints.

None.

8. Research Setting

8.1. Describe the sites or locations where your research team will conduct the research.

Recruitment, screenings, health questionnaires, subject measurements and phlebotomy will be conducted at the CTSC Clinical Research Unit.

Cell purification and culturing from blood will be conducted at the CTSC T1 laboratory, while LC3 cell treatment and analysis will be conducted in the laboratories of [name], in the Department of Molecular Genetics and Microbiology, [name].

8.2. Identify where your research team will identify and recruit potential subjects.

We will recruit potential subjects with prediabetes from the Endocrinology Clinics, from the CTSC participant recruitment service, and from the UNM Prediabetes Cohort Registry (HRRC # 11-422). These latter subjects agreed to be contacted in the event of future research involving prediabetes. We will also employ CTSC-sponsored social media to recruit for this study, if necessary. We do not anticipate having difficulty identifying subjects who are interested in participating in this study. We estimate that 50 adults at risk for diabetes will need to be screened to find 30 eligible subjects with prediabetes to enroll in this study.

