8.3. Identify where research procedures will be performed including any laboratory analytics

Study subject interviews, body measurements and phlebotomy will be conducted at the CTSC Clinical Research Unit.

Measurements of A1c, creatinine, fasting blood glucose, electrolytes, and insulin will be conducted in the CTSC Clinical Research Unit using the CTSC Clinical Laboratory or Tricore Laboratory.

Cell purification and culturing from subject's blood draw will be conducted utilizing dedicated bench space in the CTSC T1 laboratory. Cell purification will carry along no personal identifiers, only the blinded numeric assignment, and utilize Ficoll gradient separation for isolation of the mononuclear layer. The services of the T1 Lab will also be used for subsequent RNA purifications, cDNA production, qRT-PCR, DNA Methylation measurements, and assay quantifications.

Cultured cells labeled with the blinded numeric assigned will be transferred to the laboratories of [name], in Fitz Hall for cell treatment and analysis. Cells undergoing autophagy can be identified by visualizing fluorescently-labeled LC3 puncta and/or the co-localization of fluorescently labeled LC3 and lysosomal markers. LC3 measurements will be quantified using our Cellomics ArrayScan® VTI HCS Reader with a fully automated microscope featuring Zeiss optics for HTS high-content screening of 96

PROTOCOL TITLE: A Double-Blind, Placebo-Controlled Trial of Anti-Aging, Pro-Autophagy Effects of Metformin in Adults with Prediabetes

well plates utilizing iDev Intelligent Assay Development workflow software essential for high content analyses studies by trained personnel.

The expression of 4 autophagy genes known to be regulated by TFEB and a control will be measured and analyzed via qRT-PCR.

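### A rise in LC3 dots per cell shows more autophagosomes present, which is not by itself increased autophagy, so Aim 1 concludes more than its primary outcome can show

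*Combined protocol and SAP*

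**What the plan says.** Section 1.2, repeated in 7.1, sets Aim 1: "Demonstrate that metformin therapy will increase cellular autophagy as an inverse correlate of aging as measured by increases in LC3 and TFEB scores". The primary outcome there is "Primary outcome: Increased levels of LC3 in leukocytes".

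The assay is described in 3.1 (Sample Size Determination and Power) and repeated in 5.3 and 13.2. Cells are "cultured and adhered in full media in 96 well plates and then immunostained to detect endogenous LC3", and an automated scanner counts the dots. Autophagosome formation is said to be monitored "by quantitation of the number of LC3-labeled puncta (autophagosomes" and so on. The interpretive rule follows: "An increase in LC3 puncta formation denotes an increase in autophagic activity". Table 2 in 3.1 describes the LC3 test in the same way: "This test quantitates intracellular autophagosome formation; a marker of autophagy".

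Two places come close to a clearance readout:

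- Section 8.3 says: "Cells undergoing autophagy can be identified by visualizing fluorescently-labeled LC3 puncta and/or the co-localization of fluorescently labeled LC3 and lysosomal markers". This is optional, and it does not enter the primary outcome, Table 2, the power statement or the analysis.
- Section 8.1 says "LC3 cell treatment and analysis will be conducted in the laboratories of" the autophagy laboratory, and 8.3 also mentions cell treatment. The treatment is not defined anywhere.

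TFEB is a secondary outcome for Aim 1, stated as not powered in 3.1. According to 8.3 it is the expression of four TFEB-regulated genes and a control, by qRT-PCR.

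**The concern.** The rule in 3.1 speaks of puncta formation, and Table 2 says that formation is what the test quantifies. What is measured is the number of puncta in a fixed image. A number present at one moment depends on how fast the structures are made and how fast they are removed. Section 2.1 describes autophagy as a recycling process, so removal is part of what Aim 1 is about.

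Two errors are possible if the plan is followed as written. A significant rise in dots would be reported as increased autophagy even if clearance had only slowed. A real rise in turnover that speeded formation and clearance together would leave the count little changed and would be reported as a null result. This matters more than usual because section 1.1 gives the primary objective as validating the autophagy design in humans, as preliminary data for a later proposal.

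**Working it through.** **Inputs from section 3.1.** Change in LC3 of 8 ± 4 (metformin) and 3 ± 4 (placebo) dots per cell; baseline 2 in both arms; 12 analysed per group; two-tailed unpaired t-test at 0.05; stated power 0.83 (printed as beta).

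**Step 1: reproduce the plan's figures.** Enrolment: 30 × 0.80 / 2 = 12 per group. Standard error of the difference: 4 × √(2/12) = 1.633. Noncentrality: 5 / 1.633 = 3.06 on 22 degrees of freedom. Power by the noncentral t is 0.833, which agrees with 0.83. The arithmetic of the power statement is sound and is not in dispute.

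**Step 2: implied Week 12 means.** Placebo 2 + 3 = 5; metformin 2 + 8 = 10. Because baselines are assumed equal, the difference in change equals the difference in Week 12 means, 5 dots.

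**Step 3: what that difference can mean.** Assume a steady state in which dots N = F/k, where F is the formation rate and k the clearance rate constant. Turnover is then kN = F. The multiples below are relative to placebo and are illustrative. The SD is held at 4 throughout.

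| Case | Formation | Clearance | Turnover | Dots, metformin | Difference from 5 | Power |
|---|---|---|---|---|---|---|
| a | ×2 | ×1 | ×2 | 10 | 5 | 0.83 |
| b | ×1 | ×0.5 | ×1 | 10 | 5 | 0.83 |
| c | ×0.5 | ×0.25 | ×0.5 | 10 | 5 | 0.83 |
| d | ×2 | ×1.25 | ×2 | 8 | 3.0 | 0.42 |
| e | ×2 | ×1.5 | ×2 | 6.7 | 1.7 | 0.16 |
| f | ×2 | ×2 | ×2 | 5 | 0 | 0.05 |

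Cases a to c are identical to the planned test although turnover differs fourfold between a and c. In cases a, d, e and f turnover doubles each time, yet power falls from 0.83 to the type I error rate. A larger sample would not separate a, b and c.

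**Step 4: would lysosomal co-localisation settle it?** In the same model the co-localised signal is also a stock, F/d, where d is the rate of degradation inside the lysosome. In case b, F is unchanged, so the co-localised signal stays flat while dots double. If d falls, the co-localised signal rises. A rule that accepts increased autophagy when dots rise and co-localised LC3 does not fall would therefore pass case b, the slowed-clearance case it is meant to catch.

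**Step 5: would paired wells settle it?** Suppose a block stops clearance for a short time T and formation continues. The blocked count is F/k + F·T and the unblocked count is F/k. The difference is F·T, and k cancels. Relative to placebo it is ×2 in case a, ×1 in b, ×0.5 in c and ×2 in f, which matches turnover in each. This assumes a complete block that does not itself alter formation.

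**The case against.** The strongest defence has five parts.

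- **Aim 1 does not rest on LC3 alone.** It names TFEB as well, and TFEB gives supporting evidence on induction. That stands. But TFEB is unpowered, measures gene expression and not clearance, and no rule links it to the conclusion drawn from LC3.
- **The undefined cell treatment may already be a lysosomal block.** The documents cannot exclude this. The assay text in 3.1 describes no such condition, however, and no outcome uses one, so the plan should say.
- **LC3 is measured at Weeks 0, 4 and 12.** True, but repeating a static count does not measure turnover.
- **This is a 30-subject pilot, and the protocol calls LC3-II a widely used marker.** That supports keeping dots per cell as the powered outcome. It does not support the wider conclusion, and a pilot meant to validate the design is a good place to settle what its readout means.
- **The rates in the table are invented.** They are. The powers in cases d and e follow from the chosen multiples and are not evidence about this trial. That a count depends on both formation and removal does not rest on them.

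A reader might also infer that a positive result could mean the opposite of Hypothesis 1. The documents do not support going that far. Hypothesis 1 is about surrogate measures of autophagy and aging. A true reversal needs something like case c, and nothing in the protocol suggests that metformin slows clearance. The mechanism it offers runs through AMPK and upstream regulation (2.1 and 2.2).

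**Conclusion.** The point holds as one of measurement validity. As planned, a significant rise in dots per cell supports the statement that autophagosome number increased. It does not by itself support the statement that autophagy increased. Nothing now in the Aim 1 outcome or analysis closes that gap: co-localisation is optional, the cell treatment is undefined, and TFEB is unpowered and does not measure clearance.

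The size depends on rates that the documents do not give. Under the steady-state assumption with SD 4, the planned 5-dot difference is detected with power 0.83 whether turnover doubles, stays the same or halves. A true doubling of turnover is detected with power anywhere from 0.83 down to 0.05, depending on how far clearance rises with it. Which of these metformin would produce cannot be decided from the documents. The sample size itself needs no correction on this account.

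**What to change.** 1. Keep the change in dots per cell as the powered Aim 1 outcome.
2. In 3.1, 5.3 and 13.2, replace the sentence equating puncta formation with autophagic activity, and the LC3 entry in Table 2, with: *LC3 dots per cell measures autophagosome number.* Report a rise in dots alone as *increased autophagosome number*.
3. Allow the conclusion *increased autophagy* only if paired wells from the same sample, with and without a short lysosomal block, show a larger change in the blocked-minus-unblocked difference on metformin than on placebo. Analyse that difference with the same t-test, as an unpowered secondary outcome. The documents give no SD for it, so a non-significant result should be called inconclusive.
4. State in 8.1 and 8.3 whether the cell treatment is this block and, if not, what it is.
5. Do not use a rule that co-localised LC3 must not fall as the test of increased autophagy, because it passes the slowed-clearance case (step 4).

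The cost is some extra wells, reagent and image analysis, and a narrower claim from dots alone. The documents do not give cell yield, so capacity for the extra wells is an assumption that the laboratory must confirm. If the wells are not feasible, items 1, 2 and 4 still apply and cost nothing beyond the rewording, and Aim 1 then makes no claim of increased autophagy from LC3.
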